11. ASSESSMENTS

11.1 Vital Sign Measurements

Subject should rest for at least 5 minutes before assessment. For younger subjects with whom this may not be possible, attempts should be made to measure vital signs when subject is calm. The following vital signs should be measured:

- Heart Rate
- Blood Pressure
- Respiratory Rate
- Body Temperature

11.2 Weight Measurement

Weight should be measured at each visit by the same auxologist at approximately the same time of day on the same calibrated weight scale (to minimize bias and reduce variability). Subjects should be wearing light clothing and no shoes. For subjects who cannot stand independently, a calibrated pediatric/infant weight scale should be used.

11.3 Height Measurement

Height should be measured at each visit by the same auxologist at approximately the same time of day using the same wall-mounted stadiometer (to minimize bias and reduce variability), the accuracy of which has been verified prior to each visit using a 100 cm metallic calibration rod. Children < 2 years old should be measured in a recumbent position using a length board placed on a flat, stable surface such as a table. Note: despite previous height measurements being performed on a length board, once a subject is 2 years old, the subsequent measurements should be performed on a stadiometer.

For subjects ≥ 2 years old, obtain height measurements on a stadiometer following the general guidance below:

- The subject should not stretch prior to height determination
- The subject should be standing without shoes and socks. Thin foot covers over bare feet may be worn
- The subject should be wearing only light clothing so that the subject's pose can be observed
- The subject's gaze should be forward and horizontal position (Frankfort plane)
- The subject's heels should be placed together. If the subject has genu valgum (knock-knee), the knees must be in contact with each other and the heels as close to each other as possible
- The subject's heels, buttocks, shoulders, and occiput of the cranium should all be in contact with the stadiometer
- Upward pressure should be applied to the subject's mandibular rami (jaw)
- The subject's shoulders should be relaxed and pressure applied to the abdomen to reduce lordosis (spine curvature)
- The counterweight head is lowered until it is in contact with the highest part of the subject's head
- The height measurement is read at the horizontal level with the counter
- The subject should step away from the stadiometer and **repeat the previous steps 2 more times**. Repeated determinations must be within 0.5 cm of each other otherwise three new measurements must be performed and recorded.

For subjects < 2 years old, obtain height measurement on a length board following the general guidance below (*WHO 2008*):

- The subject should be undressed (diaper/underwear is acceptable)
- The parent/legal guardian/caregiver or another individual should place the subject supine on the length board with the subject's head against the fixed headboard, compressing the hair
- The subject's head should be positioned so that an imaginary vertical line from the ear canal to the lower border of the eye socket is perpendicular to the board. The subject's eyes should be looking straight up
- The auxologist should stand on the side of the length board, clearly able to see the measuring tape. If possible, the subject's parent/legal guardian/caregiver or another individual should stand behind the headboard and hold the subject's head in position
- The subject should lie straight along the board, with shoulders touching the board and without arching the spine
- The subject should not change position during measurement
- Gentle pressure should be applied to the subject's knees to straighten the legs as far as possible
- While the subject's knees are being held with one hand, the footboard should be pulled with the other hand until flat against the subject's feet, toes pointing upwards
- Measurement of the subject's length is read and recorded in centimeters to the last completed 0.1 cm

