8.1 Trial Entry Criteria

8.1.1 Inclusion Criteria

- 1) Investigator-determined GHD diagnosis together with at least one of the following prior to the historical initiation of daily hGH therapy:
 - a. 2 GH stimulation test(s) with peak GH level of ≤ 10 ng/mL
 - b. Impaired height defined as at least one of the following:
 - i) ≥ 2 SD below the mean height for chronological age and sex when compared to the relevant growth charts:
 - (1) 2006 WHO Child Growth Standards for < 2 years old

- (2) 2000 CDC Growth Charts for the United States for ≥ 2 years old
 - ii) ≥ 1.5 SDS below mid-parental height
 - c. IGF-1 level ≥ 1 SD below the mean IGF-1 level standardized for age and sex according to the local laboratory reference values
 - d. Bone age x-ray ≥ 6 months less than chronological age
 - e. Diagnosis of at least one additional pituitary hormone deficiency
 - f. Congenital hypopituitarism due to congenital hypothalamic-pituitary defect (eg, ectopic posterior pituitary, pituitary hypoplasia, abnormal stalk, septo-optic dysplasia) or genetic defect (eg, GH1, POU1F1, or PROP1)
- 2) 6 months to 17 years old, inclusive, at Visit 1
 - a. If 3 to 17 years old, are taking daily hGH at a dose of ≥ 0.20 mg hGH/kg/week for at least 13 weeks but no more than 130 weeks prior to Visit 1
 - b. If ≥ 6 months but < 3 years old, are either hGH treatment-naïve or are taking daily hGH at a dose of ≥ 0.20 mg hGH/kg/week for no more than 130 weeks prior to Visit 1
- 3) Tanner stage < 5 at Visit 1
- 4) Open epiphyses (bone age ≤ 14.0 years for females or ≤ 16.0 years for males)
- 5) Written, signed, informed consent of the parent or legal guardian of the subject and written assent of the subject as required by the IRB/HREC/IEC

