5.3. VISIT WINDOW

Enrolled subjects will attend a total of 3 morning trial visits:

- Visit 1 will be considered Week 1, Day 1 (first day/week of dosing)
- Visit 2 will be performed during Week 13 (± 1 week), 5 days (± 1 day) post-dose
 - If during Week 12, Visit 2 must occur on Days 82 to 84
 - If during Week 13, Visit 2 must occur on Days 89 to 91
 - If during Week 14, Visit 2 must occur on Days 96 to 98
- Visit 3 will be performed during Week 26 (± 1 week), 5 days (± 1 day) post-dose
 - If during Week 25, Visit 3 must occur on Days 173 to 175
 - If during Week 26, Visit 3 must occur on Days 180 to 182
 - If during Week 27, Visit 3 must occur on Days 187 to 189

Subjects <3 years old at Visit 1 will have a total of 4 morning trial visits including the above 3 visits and the addition of:

- C_{max} Visit to be performed during Week 4 (+1 week), 1-2 days after the 4th or 5th dose
 - If during Week 4, C_{max} Visit must occur on Days 23-24
 - If during Week 5, C_{max} Visit must occur on Days 30-31

Post-baseline unscheduled visit (occurred after the date of initiation of the first dose) or end of study visit (early termination visit) will be mapped to the post-baseline scheduled visit with the closest target study day for each scheduled assessment according to [Table 2](#). If the unscheduled visit is in the middle of two scheduled visits, map it to the later one. After mapping, if there are more than one visit in the same window, the visit closer to the target assessment day will be used. If more than one visit has the equal distance to the target day then the later one will be used, if more than one visit on the same day, use the time or the sequence number to select the later record. For listings and shift tables, all data points will be included.

Table 2: Analysis Window

Visit	Screening	Visit 1	C _{max} Visit	Visit 2	Visit 3/ET
Week	Weeks -4 to -1	Week 1	Week 4 (+ 1 Week)	Week 13 (± 1 Week)	Week 26 (± 1 Week)
Target Day		Day 1	Day 29	Day 92	Day 183
Range		Day 1	Day 2 - 60	Day 61 - 137	Day 138 - EOS

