5.4. DERIVED AND COMPUTED VARIABLES

[Table 3](#) provides the rules for derived and computed variables which have been initially identified as important for the analysis of the safety, efficacy or PK/PD as appropriate. It is expected that additional variables will be required. The SAP will not be amended for additional variables that are not related to the primary target or key secondary target variables. Any additional derived or computed variables will be identified and documented in the SAS programs that create the analysis files.

The birth date for each subject is collected on the eCRF. To be consistent with all the other TransCon hGH studies, the 15th day of the reported month is used to calculate the age and related scores. In such case, all the height SDS for the subjects will be calculated using 15th as the birth day. The HSDS reported in the eCRF will not be used as it is based on the actual birth date reported by the subject. FMD K&L will utilize the published SAS macro to calculate the height SDS and no independent QC is required for published SAS macro.

Table 3: Parameter Definition

Parameter	Definition
Annualized Height Velocity at visit x (HV) cm/year	$((\text{Height (Visit } x) - \text{Height (Visit } 1)) * 365) / (\text{Date (Visit } x) - \text{Date (Visit } 1))$
Height Standard Deviation Score (HSDS)	Height SDS will be derived using CDC 2000 (United States of America). A standard SAS program is published at: https://www.cdc.gov/nccdphp/dnpao/growthcharts/resources/sas.htm
Change from baseline over 26 weeks	The value of each variable at each post-baseline time point minus the baseline score.
Normalized serum IGF-1 SDS	Proportion of subjects with IGF-1 Standard Deviation Score (SDS) of 0 to +2.0. Also derive for -2.0 to +2.0, -1.0 to +2.0.
Parents' Height SDS	$((\text{Parents Height}/M)^L - 1) / (L * S)$ Where M=median, S= generalized coefficient of variation, and L= power in the Box-Cox transformation, the M, S, L values are obtained from the CDC website; Percentile Data Files with LMS Values
Total Duration of Treatment (day)	Last treatment date – first treatment date +7
Total Duration of Treatment (week)	Round (Total Duration of Treatment in days/7) to the nearest integer
Treatment Compliance	Total Number of Dose Taken/Total Duration of Treatment (week)

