9. EFFICACY ANALYSES

9.1. ANNUALIZED HV

Annualized height velocity is calculated based on the rules stated in [Section 5.4](#). An ANCOVA will be used to analyze by visit annualized height velocity. The model will include baseline age, peak GH levels (log transformed) at diagnosis, delta mid-parental height SDS, prior GH dose level (log transformed), and duration (log transformed) as covariates, and gender as a factor.

Summary tables including data and listings will be presented for all height measured during the trial.

9.2. ΔHSDS

Height Standard Deviation Score (HSDS) is derived based on the rules stated in [Section 5.4](#). The by visit change from baseline of the HSDS will be analyzed by ANCOVA model including baseline age, peak GH (log transformed) at diagnosis, delta mid-parental height SDS, prior GH dose level (log transformed), and duration (log transformed) as covariates, and gender as a factor.

Summary tables and Figures will be provided for HSDS and change from baseline in HSDS at each time point. Listings will also be generated for all the HSDS information.

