9.4. SUBGROUP ANALYSIS

Efficacy variables including annualized HV, HSDS and IGF-1 SDS may also be summarized based on the following subgroups if the sample size allows.

- Age (<3 years, >=3 to <6 years. [≥ 6 to <11 years for girls, ≥ 6 to <12 years for boys] and [≥ 11 years for girls, ≥ 12 years for boys])
- Gender
- Baseline GH-stim strata (≤ 5 ng/mL and >5 ng/mL)
- Prior exposure to hGH therapy (Yes/No)

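### For children who turn 2 on study, annualized height velocity subtracts a recumbent length from a standing height, and the SAP has no rule for this

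*Protocol*

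**What the plan says.** Protocol 11.3 fixes the method by age on the day of measurement. Below 2 years: "Children < 2 years old should be measured in a recumbent position using a length board". From the second birthday, even if earlier values came from the length board: "once a subject is 2 years old, the subsequent measurements should be performed on a stadiometer".

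SAP 5.4, Table 3, defines "Annualized Height Velocity at visit x (HV) cm/year" as the height at Visit x minus the height at Visit 1, times 365, divided by the days between the two visits. The formula has no term for method. The model in SAP 9.1 has none either: "The model will include baseline age, peak GH levels (log transformed) at diagnosis, delta mid-parental height SDS", followed by prior GH dose, its duration, and gender.

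Eligibility is "6 months to 17 years old, inclusive, at Visit 1" (Protocol 8.1.1), so a child can pass the second birthday between Visit 1 and Visit 3. SAP 9.4 has an under-3 age group, but only as an option: "Efficacy variables including annualized HV, HSDS and IGF-1 SDS may also be summarized", if the sample size allows.

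Neither document gives a conversion from length to height, a paired reading, a flag for a change of method, or a sensitivity analysis.

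**The concern.** HV is meant to measure growth. When the first value is a length and the second a standing height, the difference also contains the gap between the two methods, and annualizing multiplies that gap by about 2 at Week 26 and about 4 at Week 13. A site that follows the protocol exactly will produce such values.

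This sits badly with the protocol's own aims. Section 11.3 asks for the same stadiometer at each visit to limit bias and variability, and 7.1.2 asks for assessments to be done in a similar way each time. At stake are the individual HV values of the affected children and, if it is produced, the HV mean of a young cohort whose size is not fixed and which the protocol expects to be hard to recruit.

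**Working it through.** **No plan figure to reproduce.** The documents state neither the length-height gap nor its effect on HV. The only design figure is the chance of seeing an AE of 2% incidence in 150 subjects: 1 − 0.98^150 = 0.952. It reproduces, and nothing below depends on it.

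**Inputs from the documents**
- HV = (Height at Visit x − Height at Visit 1) × 365 / (days between visits): SAP Table 3.
- Visit 1 is Day 1. Nominal Week 13: "If during Week 13, Visit 2 must occur on Days 89 to 91". Nominal Week 26: "If during Week 26, Visit 3 must occur on Days 180 to 182". The full windows are Days 82–98 and 173–189 (SAP 5.3).
- Length is read down to the last completed 0.1 cm (Protocol 11.3).

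**Assumptions**
- Gap *d*: length exceeds standing height in the same child by 0.3 to 1.0 cm on average.
- For the share affected: ages at Visit 1 uniform over 6–36 months in the under-3 cohort.

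**Step 1. Shift per affected child** = −*d* × 365 / (visit day − 1)

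| Gap *d* (cm) | Week 26, Day 182 (365/181 = 2.02) | Week 13, Day 91 (365/90 = 4.06) |
|---|---|---|
| 0.3 | −0.60 cm/year | −1.22 cm/year |
| 0.5 | −1.01 | −2.03 |
| 0.7 | −1.41 | −2.84 |
| 1.0 | −2.02 | −4.06 |

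Over the full windows the factor runs from 1.94 to 2.12 at Visit 3 and from 3.76 to 4.51 at Visit 2.

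**Step 2. Rounding.** Reading length down loses about 0.05 cm on average at Visit 1. This raises HV by 0.05 × 2.02 = 0.1 cm/year at Week 26 and 0.05 × 4.06 = 0.2 cm/year at Week 13. It does not reverse the sign within the assumed range.

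**Step 3. Who is affected.** At Week 26, children within 181/30.44 = 5.9 months of their second birthday at Visit 1, that is, aged about 18 to 24 months. At Week 13, those within 90/30.44 = 3.0 months. Under uniform ages the shares are 5.9/30 ≈ 20% and 3.0/30 ≈ 10%. A child who turns 2 between Screening and Visit 1 is unaffected. One who turns 2 between Visits 2 and 3 has a mixed HV at Visit 3 only.

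**Step 4. Effect on means at Week 26**
- Under-3 mean, 20% crossing: 0.20 × 0.60 = 0.12 to 0.20 × 2.02 = 0.40 cm/year lower. At 10% crossing this is 0.06 to 0.20; at 40% it is 0.24 to 0.81.
- Overall mean, 2 affected among 150, *d* = 0.7: 2/150 × 1.41 = 0.02 cm/year lower.

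**The case against.** The case against rests on five points.

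- **Direction and size are not in the documents.** This stands. Nothing states that length exceeds standing height, and the stadiometer technique in 11.3 (upward pressure on the jaw, pressure on the abdomen to reduce lordosis) could narrow a gap. Repeat readings may also differ by up to 0.5 cm, so a single child's error need not have a fixed sign. A reader might infer that every such child's HV is wrong in the same direction. The documents support only a possible average shift of assumed size.
- **The under-3 table may never be produced.** This also stands. A reader might infer that the cohort is certain to be reported as its own subgroup, but SAP 9.4 leaves that open and makes it least likely when the cohort is small.
- **The largest figures fall at Week 13.** The efficacy endpoints are set at 26 weeks. Week 13 enters through the by-visit model and tables, so the Week 26 figures are the relevant ones.
- **No decision depends on it.** The trial has one arm, safety is the primary objective, and no HV hypothesis is tested. No error rate or power changes.
- **The age rule was deliberate.** Amendment 1 adopted age at measurement to align with growth-chart guidance and standard of care. That justifies how the child is measured. It does not justify subtracting one kind of reading from the other, and the SAP, written for that amendment, is silent on this.

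The mechanism survives all five. Baseline age as a covariate does not remove it, because the error is confined to a narrow band of ages around 18 to 24 months.

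**Conclusion.** The plan, followed as written, mixes two measurement methods in HV for children who pass age 2 between Visit 1 and Visit x, and nothing in either document corrects for it. With an assumed average gap of 0.3 to 1.0 cm, HV is understated by about 0.6 to 2.0 cm/year per affected child at Week 26 and 1.2 to 4.1 cm/year at Week 13. An under-3 mean, if summarized, could be 0.1 to 0.4 cm/year too low at Week 26, given uniform ages over 6–36 months. The overall mean is essentially untouched.

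Two further inferences are not supported. One is that the error can be judged against the phase 2 HV means in Protocol 5.3: those children were treatment-naïve and received ACP-001 or daily hGH, so they are no benchmark for this cohort. The other is that change in height SDS is distorted in the same way: that depends on how the cited growth-chart program treats length and stature, which the documents do not describe.

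**What to change.** Change the SAP in 5.4 and 9.1:

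1. Flag each subject whose measurement method differs between Visit 1 and Visit x, using the recorded method. Age as derived in SAP 5.4 is not a safe substitute: it sets every birthday to the 15th of the month, which can be wrong by up to 16 days (31 − 15) and can misclassify a reading near the second birthday. The documents do not show whether the eCRF holds the method; if it does not, it has to be obtained from site records.
2. Keep flagged subjects in the main HV summary and list them.
3. Add a sensitivity summary of HV restricted to same-method pairs, overall and for under 3 years if that subgroup is produced.
4. Where a length reading happens to exist at the later visit, use it for HV, since it matches Visit 1.

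Excluding flagged children from the main mean is not advised. Under uniform ages it would drop about a fifth of a cohort that is hard to recruit, all from one narrow age band.

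The cost is a small amount of extra analysis and a sensitivity estimate that rests on fewer young children. Taking paired length and standing readings prospectively would be cleaner, but it is optional and would need a protocol amendment with the approvals described in Protocol 15.9.

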11.4 Limited Physical Examination

A limited physical examination should be performed to include injection site examination to assess for local tolerability. At Screening and Visit 1, injection site examinations to the daily hGH treatment areas should be explicitly documented so as to differentiate from any new reactions that occur during the trial.

11.5 Fundoscopy

A standard fundoscopy should be performed to rule out blurred disc margins. Additional fundoscopies may be performed throughout the trial as needed at the investigator's discretion.

11.6 Pregnancy Test

Testing for hCG should be performed for female subjects of child-bearing potential.

11.7 Patient-Reported Outcome Measures

All Patient-Reported Outcomes used in this trial have been assessed for understanding by GHD patients and their parents/legal guardians/caregivers as intended by the Sponsor in a prior Cognitive Debriefing study per the **Guidance for Industry – Patient-Reported Outcome Measures: Use in Medical Product Development to Support Labeling Claims** (*Guidance for Industry 2009*).

11.7.1 Preference Questionnaire

The Preference Questionnaire should only be completed for subjects who were treated with daily hGH prior to enrollment in the trial. The parent/legal guardian/caregiver will complete the PQ-P, while the subject, if ≥ 9 years old at Visit 1, will complete the PQ-C.

At Week 6, immediately prior to the 6th dose of study drug, the PQ-P and PQ-C (as applicable) will be completed within the Subject Diary. At approximately Week 13, the PQ-P and PQ-C (as applicable) will be completed at Visit 2.

11.7.2 Child Sheehan Disability Scale

At Visit 1, the Child Sheehan Disability Scale (CSDS) should only be completed for subjects who were treated with daily hGH prior to enrollment. At all other time points, the CSDS should be completed for all subjects.

The CSDS is an adaptation of the Sheehan Disability Scale to assess impairment related to childhood anxiety on children and their parents (*Whiteside 2009*). This measure is being adapted in this trial to assess impairment related to treatment burden on children and their parents/legal guardians/caregivers. The parent/legal guardian/caregiver will complete the CSDS-P, while the subject, if ≥ 9 years old at Visit 1, will complete the CSDS-C.

At Week 6, immediately prior to the 6th dose of study drug, the CSDS-P and the CSDS-C (as applicable) will be completed within the Subject Diary. At approximately Week 13 and Week 26, the CSDS-P and the CSDS-C (as applicable) will be completed at Visits 2 and 3.

11.7.3 Convenience & Overall Satisfaction Domains of the Treatment Satisfaction Questionnaire for Medication

At Visit 1, the Convenience and Overall Satisfaction (C&OS) of the Treatment Satisfaction Questionnaire for Medication (TSQM-9) should only be completed for subjects who were treated with daily hGH prior to enrollment. At all other time points, the C&OS should be completed for all subjects.

The original 14-item Treatment Satisfaction Questionnaire for Medication (TSQM) Version 1.4 is a reliable and valid instrument to assess patients' satisfaction with medication, providing scores in four domains – Side Effects, Effectiveness, Convenience and Overall Satisfaction. In naturalistic studies, administering the TSQM with the Side Effects domain could provoke the physician to assess the presence or absence of adverse events in a way that is clinically atypical, carrying the potential to interfere with routine medical care. As a result, an abbreviated 9-item TSQM (TSQM-9), derived from the TSQM Version 1.4 but without the Side Effects domain was created ([Bharmal 2009](#)). This measure is being adapted further for this trial with the removal of the Effectiveness domain since effectiveness of hGH is not subjective and will be assessed with objective measures in this and other trials evaluating TransCon hGH. Thus, only Convenience & Overall Satisfaction domains (C&OS) of the TSQM will be used. Only the parent/legal guardian/caregiver will complete the C&OS of the TSQM-9, thus it has been identified for this trial as the C&OS – Parent (C&OS-P).

At Week 6, immediately prior to the 6th dose of study drug, the C&OS will be completed within the Subject Diary. At approximately Week 13, the C&OS will be completed at Visit 2.

